## 2.0 STUDY OBJECTIVES AND ENDPOINTS

### 2.1 Primary Objective and Endpoint

Primary Objective	Primary Endpoint
To estimate the prevalence of SARS-CoV-2 IgG seropositivity among individuals in communities surrounding selected NIAID clinical research sites	Proportion of individuals who have SARS-CoV-2 IgG antibodies, evaluated overall and by age strata, in the following populations: 
 
1) Adults 18 and older residing in senior living facilities
 
2) Adults 18 and older attending outpatient healthcare clinics, and
 
3) Individuals in communities of selected research sites in the following age categories               
 
a. 2 months – 17years old
 
b. 18-39 years old
 
c. 40-59 years old
 
d. 60 years and older
 
 
 

### 2.2 Secondary Objectives and Endpoints

Secondary Objectives	Secondary Endpoints
1) To estimate prevalence of SARS-CoV-2 infection based on results of SARS-CoV-2 RNA testing	Proportion of individuals with SARS-CoV-2 infection (based on SARS-CoV-2 RNA testing)
2) To estimate prevalence of SARS-CoV-2 infection by presence versus absence of symptoms consistent with COVID-19	Proportion of individuals with SARS-CoV-2 infection (based on SARS-CoV-2 RNA testing) who report lack of symptoms versus presence of symptoms consistent with COVID-19
3) To estimate seroprevalence of SARS-CoV-2 among: 
 
a) Those without past or current symptoms consistent with COVID-19,
 
b) Those with no prior positive SARS-CoV-2 testing, but who report close contact with confirmed or presumed cases, and
 
c) Those with history of co-morbid medical conditions
 
	Proportion of individuals with SARS-CoV-2 IgG antibodies who report: 
 
a) Prior confirmed or presumed COVID-19 vs. those who report never having symptoms,
 
b) No prior COVID-19 but who report close contact with a COVID-19 case (as defined by the US Centers for Disease Control and Prevention), and
 
c) Co-morbid medical conditions such as obesity, hypertension and diabetes
 

Secondary Objectives	Secondary Endpoints
4) To assess association between demographic, clinical and social factors with SARS-CoV-2 infection and seroprevalence	Socioeconomic, demographic and clinical correlates of COVID-19 and/or SARS-CoV-2 seroprevalence with particular interest in racial and ethnic health disparities
5) To estimate potential size of populations for referral to COVID-19 prevention and treatment studies	Extrapolated population sizes of 
 
a) Those with active COVID-19,
 
b) Those who have serologic evidence of recent and/or past SARS-CoV-2 infection, and
 
c) Those who have negative RNA and serologic SARS-CoV-2 tests
 

6) To assess knowledge, attitudes, and behavior about SARS-CoV-2 and COVID-19	Knowledge and attitudes about SARS-CoV-2 and COVID-19, and uptake of public health interventions including shelter in place orders, social distancing, and mask use
7) To assess performance characteristics of PCR-based and serologic SARS-CoV-2 tests using saliva	
 
a) Estimates of sensitivity, specificity, and concordance of SARS-CoV-2 assays using saliva samples, compared to nasal swab and serum samples
 
b) Estimates of sensitivity and specificity of SARS-CoV-2 IgG serologic assays using saliva samples, compared to serum samples
 

### 2.3 Exploratory Objectives

Exploratory Objective 1:

- To model epidemiologic impact over time of COVID-19 in the study communities, including modeled incidence and prevalence of COVID-19.

Exploratory Objective 2:

- To conduct laboratory testing in a subset of participants to characterize SARS-CoV-2 viruses and the host response to SARS-CoV-2 infection, which may include detection of anti-SARS-CoV-2 IgM antibodies. This testing may also include phylogenetic analysis of SARS-CoV-2 and co-infections with other viruses, including viruses that impact the specificity of SARS-CoV-2 serologic assays.

### 3.0 STUDY POPULATION

The study population will consist of adults residing in senior living facilities or attending outpatient healthcare facilities, and adults and children in select neighborhoods of research site communities.

Study staff will be in full personal protective equipment to minimize transmission risks and mitigate access restrictions. Masks will be offered to all participants who are not wearing them. Tablets, seating areas, and other surfaces will be sanitized with appropriate disinfectants between study participants. Each site will be required to document risk mitigation procedures in site standard operating procedures or other procedures manuals.

### **3.1 Inclusion Criteria**

#### **3.1.1 Adults residing in senior living facilities or attending outpatient healthcare facilities**

**3.1.1.1** At least 18 years of age

**3.1.1.2** Willing and able to provide informed consent or consent has been provided by legal representative (for those with mental incapacity in senior living facilities)

**3.1.1.3** Recruited from a selected facility

#### **3.1.2 Adults and children from select neighborhoods of research site communities**

**3.1.2.1** Adults and children > 2 months of age

**3.1.2.2** For individuals < 18 years old, a guardian must be present (in person or by phone for those 15 – 17 years old)

**3.1.2.3** Willing and able to provide consent (or assent for individuals 7-17 years old, parent/guardian will provide consent for all minors)

**3.1.2.4** Recruited from a selected venue

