### **3.2 Exclusion Criteria**

**3.2.1** Previous enrollment in this study, either from the same or another CRS community.

**3.2.2** Any condition that, in the opinion of the study staff, would make participation in the study unsafe, complicate interpretation of study outcome data, or otherwise interfere with achieving the study objectives.

Note – COVID-19 vaccination is not exclusionary

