### **3.3.1 Sampling Design and Recruitment at Community Venues**

The initial sampling “universe” – the list of target venues in the catchment area of the CRS – is comprised of venues routinely frequented by residents of the community. A venue could be retail businesses (e.g., laundromats, grocery stores), cafes and restaurants, health clubs, social service providers, schools, places of worship, transit hubs, parks, or beaches. Once this list (the “universe”) of potential venues is created, CRS staff will determine the suitability of each venue. A venue may not be suitable for sampling if any of the following are true:

- It would be impossible logistically to recruit, interview and conduct study procedures.
- Venue owner(s) refuse to allow the project staff access to venue attendees.

Project staff will assess venue suitability by observing venues or informally talking to residents of the community and venue owners/managers. Time-location sampling will be used to select individuals who attend the population of suitable community venues in the catchment area during the overlapping operating hours of both the community venues and the CRS staff. For each catchment area, we first create a list of all suitable community venues and times that each venue is available in a given calendar period, e.g. week. Sampling will be performed in two stages. The first stage selects a stratified random sample of Venue Day Times (VDTs; approximate 4-hour time block that is available for recruitment at a specified venue). The second stage samples individuals from sampled VDTs (details outlined in the SSP Manual).

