### **3.6 Community Definition**

The target venues for recruitment, enrollment, and data collection will be within the surrounding zip codes of the CRS. The protocol team will work with CRSs to select enough zip codes to include a specified number of residents that will allow for rapid enrollment of a representative sampling of the community. Details of the approach and documentation of the final selections will be documented in the SSP Manual.

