### **6.3 Statistical Analyses**

This section briefly describes the final study analyses. Detailed technical specifications of the statistical analyses will be described in a separate Statistical Analysis Plan (SAP).

All statistical analyses will account for the sample design to create the base sampling weights. The sampling weights will be further adjusted for nonresponse and post-stratified using demographic information such as age, sex, race/ethnicity, education, and income. County-level estimates from the census bureau will be used for raking and post-stratification. We will estimate prevalence and calculate 95% confidence intervals of SARS-CoV-2 infection and IgG seropositivity for each target population separately, i.e. among community residents in each of the age groups (2 months-17, 18-39, 40-59, 60+ years); among patients attending the outpatient clinics; and among senior living facility residents.

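### Section 6.3 reports resident prevalence raked to the county, but the target community is a ZIP-code catchment and no stated rule ties participants to either area

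*Protocol*

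**What the plan says.** **Estimand and weighting.** Protocol 6.3 will report prevalence and 95% confidence intervals "among community residents in each of the age groups (2 months-17, 18-39, 40-59, 60+ years"). It fixes the calibration source: "County-level estimates from the census bureau will be used for raking and post-stratification". The adjustment variables it gives as examples are age, sex, race/ethnicity, education and income.

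**Target area.** Section 1.1 defines the community as the area around each clinical research site (CRS) and says the weighting is meant to make estimates representative of the CRS communities. Section 3.6 draws that area by ZIP code, but the sentence locates venues: "The target venues for recruitment, enrollment, and data collection will be within the surrounding zip codes of the CRS". The number of ZIP codes is left open; the aim is to "select enough zip codes to include a specified number of residents that will allow for rapid enrollment of a representative sampling of the community".

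**Who can enter.** Section 3.1.2 lists age, guardian presence, consent or assent, and "Recruited from a selected venue". Section 3.2 excludes "Previous enrollment in this study, either from the same or another CRS community" and, at staff discretion, conditions that would compromise safety or interpretation. Screening in 4.1.1 asks about age, earlier enrolment and interest.

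**Where they are found.** Under 3.3.1 the venue universe "is comprised of venues routinely frequented by residents of the community", and the permitted types include "places of worship, transit hubs, parks, or beaches".

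**Mixed description.** Section 6.1 says the study is of people living near the sites, then in the same sentence defines the community group by attendance at listed venues. Sections 2.1 and 6.3.1 speak of individuals. Section 1.2 says the method represents people taking part in social activity in the communities. Section 4.3 collects geographic indicators without giving them a role in eligibility or weighting.

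**The concern.** Three populations appear under one estimate: people who attend venues, people who live in the ZIP-code catchment, and people who live in the county. The sampling delivers the first, 1.1 and 3.6 promise the second, and the raking rule in 6.3 represents the third.

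This affects the primary community seroprevalence. It also affects the Objective 5 population sizes, which depend directly on the population that the weights represent. Larger samples do not remove an error of this kind. The visitor mix can differ between sites, because each site has its own venue list. Section 1.2 allows two or more sites in a large metropolitan area. Any that share a county would be raked to identical margins even though their catchments differ.

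**Working it through.** **1. The plan's own sample size.** Inputs from 6.2: prevalence 5%, margin 2.5 points, 95% confidence, design effect 2.5.

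n = 2.5 × 1.96² × 0.05 × 0.95 / 0.025² = 729.88, rounded to 730.

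This agrees with Table 2, and every other cell of Tables 1 and 2 also reproduces. Four strata give 2,920. None of these figures is in dispute.

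**2. The two mismatches, side by side.**

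| Element | Area or population | Section |
|---|---|---|
| Community | Area around the CRS, by ZIP code | 1.1, 3.6 |
| Claimed representation | CRS communities | 1.1 |
| Raking totals | County | 6.3 |
| Reported group | Community residents | 6.3 |
| Group sampled | Venue attendees | 3.3.1, 6.1 |
| Residence criterion or question | None stated | 3.1.2, 3.2, 4.1.1 |

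**3. Area mismatch (all inputs assumed).** Suppose a higher-prevalence group makes up 40 to 60% of the catchment but 30% of the county, and it is one of the raking categories.

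Shift = (county share − catchment share) × (difference in prevalence between groups).

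- Prevalence 10% against 5%: (0.30 − 0.40) × 5 = −0.5 point, to (0.30 − 0.60) × 5 = −1.5 points.
- Prevalence 25% against 10%: (0.30 − 0.40) × 15 = −1.5 points, to (0.30 − 0.60) × 15 = −4.5 points.

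With a 60% catchment share, the true catchment values are 8% and 19%. The margins at n = 730 are 1.96 × √(0.08 × 0.92 × 2.5/730) = 3.1 points and 1.96 × √(0.19 × 0.81 × 2.5/730) = 4.5 points. If the county had the larger share, the sign would reverse.

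**4. Visitor mismatch (all inputs assumed).** Bias = weighted visitor share × (visitor minus resident prevalence).

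- 10% × 2 points = 0.2 point.
- 20% × 5 points = 1.0 point.

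At 5% prevalence and n = 730, SE = 2.50/1.96 = 1.28 points. Coverage = Φ(1.96 − b/SE) − Φ(−1.96 − b/SE). This gives 94.7% for b = 0.2 and 87.7% for b = 1.0, against a nominal 95%. If the two prevalences are equal, the bias is zero.

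**5. Precision if only residents are analysed.** Margin = 1.96 × √(p(1 − p) × 2.5/n), for an assumed non-resident share of the 730.

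| Non-resident share | n left | Margin at 5% | Margin at 25% |
|---|---|---|---|
| 0% | 730 | 2.50 | 4.97 |
| 10% | 657 | 2.64 | 5.24 |
| 20% | 584 | 2.79 | 5.55 |
| 30% | 511 | 2.99 | 5.94 |

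Room before the target margin in Table 2 is missed: 730 − 730 = 0 at 5% prevalence; 730 − 346 = 384 at 10%; 730 − 490 = 240 at 15%; 730 − 615 = 115 at 20%; 730 − 720 = 10 at 25%.

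**The case against.** Reporting prevalence among residents does not require that every participant be a resident. It can be estimated in a residents' domain: 6.3.1 already uses domain estimates for age groups, 4.3 collects geographic data, and 6.3 defers technical detail to the SAP. The SSP Manual holds the sampling and community detail, and the pre-screening script was not available. Section 6.1 and the heading of 3.1.2 show that residents were intended. The resident label also rests mainly on one phrase in 6.3, since 2.1 and 6.3.1 say individuals.

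Much of this stands. A reader might infer that visitors will in fact be raked as residents. The documents do not support that, because an unseen manual or SAP could set them aside. A reader might also infer that the county is larger than the community. That is not established either: 3.6 leaves the number of ZIP codes open, and the catchment could approach a county or cross county lines. Nor does the exclusion of people enrolled at another CRS community show that many travel between catchments.

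Two things remain. The county as calibration area is stated in the protocol and conflicts with the area that 1.1 and 3.6 name, so an SAP using ZIP-code totals would depart from a stated rule. And 6.1 describes the community group in two ways that the eligibility and screening text does not reconcile.

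**Conclusion.** The point holds as an inconsistency in target population and calibration area, not as a demonstrated bias. The county rule in 6.3 does not match the ZIP-code community for which representativeness is claimed. The residence half is conditional: as written, and unless the SAP or SSP Manual says otherwise, visitors could be weighted to resident margins.

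The documents give no visitor share, no visitor prevalence, and no comparison of catchment with county, so neither the size nor the sign of either bias is known. The illustrations run from negligible against the planned margin to about as large as it. The larger values need strong assumptions. For example, a 1.0-point visitor bias with an overall prevalence of 5% and a 20% visitor share means residents at 4% and visitors at 9%. The sponsor should correct this because the correction is cheap and the estimate otherwise has no single population attached to it.

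**What to change.** - **Calibration area (6.3).** Take raking and post-stratification totals from the selected ZIP-code catchment. If only county totals are usable, state that the estimate is calibrated to the county and do not claim that it represents the CRS community.
- **Analysed population (6.3).** Estimate resident prevalence and Objective 5 sizes in the domain of participants who live in the calibration area, using the geographic data in 4.3. Add a home ZIP item if none exists. Give an all-attendee estimate as a sensitivity analysis. State a rule for participants without a fixed address, who could otherwise drop out although social service providers are among the venues.
- **Alternative.** If no residence domain is wanted, reword the reported group as venue attendees.
- **Wording.** Align 2.1, 3.1.2, 6.1 and 6.3.

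**Cost.** Text edits, possibly one questionnaire item, and a check that catchment totals exist for the raking variables. Venue sampling and enrolment stay as planned. The price is precision: state the resident-only margin openly, since at 5% prevalence any exclusion puts a stratum of 730 beyond its 2.5-point target.

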### **3.2 Exclusion Criteria**

**3.2.1** Previous enrollment in this study, either from the same or another CRS community.

**3.2.2** Any condition that, in the opinion of the study staff, would make participation in the study unsafe, complicate interpretation of study outcome data, or otherwise interfere with achieving the study objectives.

Note – COVID-19 vaccination is not exclusionary

### **3.3 Recruitment Process**

Each CRS will be responsible for enrolling up to 3,920 individuals. This will include a combination of community venues, healthcare facilities, and senior living facility residents. Most sites will enroll from all three populations whereas others may enroll from one or two, depending on capacity, however all sites must enroll participants from the community venues. Each study site will tailor community engagement and recruitment strategies to local circumstances and strategies using the recruitment guidelines outlined below and the Study Specific Procedures (SSP) Manual in order to maximize enrollment. Sites will be expected to work closely with community-based organizations or other appropriate groups with ties to the study communities.

### **3.3.1 Sampling Design and Recruitment at Community Venues**

The initial sampling “universe” – the list of target venues in the catchment area of the CRS – is comprised of venues routinely frequented by residents of the community. A venue could be retail businesses (e.g., laundromats, grocery stores), cafes and restaurants, health clubs, social service providers, schools, places of worship, transit hubs, parks, or beaches. Once this list (the “universe”) of potential venues is created, CRS staff will determine the suitability of each venue. A venue may not be suitable for sampling if any of the following are true:

- It would be impossible logistically to recruit, interview and conduct study procedures.
- Venue owner(s) refuse to allow the project staff access to venue attendees.

Project staff will assess venue suitability by observing venues or informally talking to residents of the community and venue owners/managers. Time-location sampling will be used to select individuals who attend the population of suitable community venues in the catchment area during the overlapping operating hours of both the community venues and the CRS staff. For each catchment area, we first create a list of all suitable community venues and times that each venue is available in a given calendar period, e.g. week. Sampling will be performed in two stages. The first stage selects a stratified random sample of Venue Day Times (VDTs; approximate 4-hour time block that is available for recruitment at a specified venue). The second stage samples individuals from sampled VDTs (details outlined in the SSP Manual).

### **3.3.2 Sampling Design and Recruitment at Outpatient Clinics**

Time-location sampling will be used to select individuals who attend suitable (where recruitment is feasible, and management is amenable) outpatient medical clinics in the catchment area during the overlapping operating hours of both the clinics and the CRS staff. Sampling will be performed in two stages. The first stage randomly selects Clinic Day Times (CDTs; approximate 4-hour time block that is available for recruitment at a specified clinic). The second stage samples individuals attending the clinic during the selected CDT (details outlined in the SSP Manual).

### **3.3.3 Sampling Design and Recruitment at Senior Living Facilities**

Sample and recruitment will be undertaken using a convenience sample of n=500 individuals from the total population of individuals residing in interested and consenting senior living facilities (details outlined in the SSP Manual).

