## 1.2 Study Design

Sites will be selected from existing NIAID CRSs. For most metropolitan areas, one CRS will be selected with consideration given to the population they serve. For larger metropolitan areas (e.g., New York, Chicago, Los Angeles), two or more CRSs may be selected to gain full representation of the region. Adjustments may be made to the selected CRSs as the dynamics of the pandemic shift.

The study will begin with community consultations with existing site community advisory boards and key stakeholders, including relevant experts from local health departments, local healthcare and social service providers, and caregivers for elderly and chronically ill populations. These consultations will help identify specific venues, key community attributes, appropriate social venues, and times and days when venues are likely to be well populated. The consultations will also include discussions about how best to report results of SARS-CoV-2 RNA testing, to local health departments, as required by health regulations. Advice will be sought from the community advisory boards to help develop communication and social mobilization plans that ensure high participation rates.

The study is observational in design with a single study visit. Recruitment, enrollment, and data collection will take place using two strategies: facility-based surveys of senior living facilities and time-location sampling (TLS) surveys of outpatient clinics and community venues. Facility-based surveys will begin with each research site creating a list of nearby senior living facilities that are interested in participating in the study. A census of all participating senior living facilities will be conducted to recruit up to 500 individuals per research site. Consent will be obtained from legal guardians for participants who are not able to provide consent. Medical abstraction will be performed for these participants in lieu of administering the study questionnaire.

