### **6.0 STATISTICAL CONSIDERATIONS**

#### **6.1 Review of Study Design**

This is a cross-sectional study of individuals residing within the vicinity of selected research sites in the United States who are (i) residing in senior living facilities, (ii) visiting outpatient clinics at given times; and (iii) members of the general population who attend any of the listed community venues at given times. The study aims to estimate prevalence of SARS-CoV-2 infection and IgG seropositivity separately in each of these populations (sampling strategies described above). Given that the three primary endpoints and their respective samples are independent, sites may recruit from one, two, or all three population groups, depending on site capacity (sites must enroll from at least the community venues). Consenting and assenting participants who satisfy the inclusion and exclusion criteria described in Section 3.0, will answer a brief survey and provide a blood sample and nasal mid-turbinate swab(s).

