## 6.2 Sample Size

The sample size is calculated for the primary objective, namely, to estimate the seroprevalence of SARS-CoV-2 among individuals and communities where potential COVID-19 vaccine or other prevention interventions studies may be prioritized.

A sample of up to 500 senior living facility residents will be enrolled (described above).

A separate sample of approximately 500 adults from outpatient clinical facilities will be selected according to a TLS design implemented as a two-stage random sample (described above).

The sample size for the TLS sampling was determined based on the minimum sample size needed to achieve prespecified margin of error (MOE). This framework sets a tolerance, also called the margin of error (MOE) for how close we would like the estimated prevalence  $\hat{p}$  to be from the true population prevalence  $p$ . Denoting the MOE by  $e$ , this means

$$Pr(|\hat{p} - p| \leq e) = 1 - \alpha.$$

Assuming  $\hat{p}$  can be treated as normally distributed, this statement is equivalent to setting the half-width of a  $100(1 - \alpha)\%$  two-sided confidence interval to  $e = z_{1-\alpha/2} \sqrt{V(\hat{p})}$  which results in a sample size of

$$n \approx z_{1-\alpha/2}^2 \frac{p(1-p)}{e^2}$$

Table 1 shows the sample sizes needed to achieve required sample sizes with +/-5% and +/-2.5% margin of error on estimated prevalence for a range of assumed prevalence of SARS-CoV-2 antibodies for simple random samples of infinite population size.

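### The senior-living sample has no random stage, and Sections 1.2 and 3.3.3 disagree on how it is drawn, yet Section 6.3 gives it base weights, county census calibration and design-based confidence intervals

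*Protocol*

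**What the plan says.** **Selection.** Section 1.2 starts from a list of nearby facilities that have expressed interest, and continues: "A census of all participating senior living facilities will be conducted to recruit up to 500 individuals per research site". Section 3.3.3 draws on interested and consenting facilities, but says: "Sample and recruitment will be undertaken using a convenience sample of n=500 individuals". Section 6.2 adds only "A sample of up to 500 senior living facility residents will be enrolled (described above") and so refers back to whichever description applies.

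**Target.** The first population in the primary endpoint (Section 2.1) is "Adults 18 and older residing in senior living facilities". Section 6.1 describes "individuals residing within the vicinity of selected research sites in the United States who are (i) residing in senior living facilities". Neither limits the target to participating facilities.

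**Analysis.** Section 6.3 states "All statistical analyses will account for the sample design to create the base sampling weights", followed by nonresponse adjustment and post-stratification. It gives the source of the control totals: "County-level estimates from the census bureau will be used for raking and post-stratification". The populations listed for prevalence estimates and 95% confidence intervals end with those "among patients attending the outpatient clinics; and among senior living facility residents". Section 6.3.1 repeats the approach for each of the three target populations: survey weights post-stratified to census data, linearization and jackknife variances, and confidence intervals built from the design-based standard errors. The only analysis excused from the sampling design is assay performance (Section 6.3.2).

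**The concern.** A base weight is the inverse of a known inclusion probability, and a design-based interval takes its validity from the random selection that produced the sample. A convenience sample supplies neither. A census of volunteer facilities supplies an inclusion probability of 1 inside those facilities and says nothing about the rest.

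Calibration is a separate problem. Raking to county totals pulls the sample towards the composition of county residents, whereas the estimate is meant for people living in nursing homes and in assisted or independent living. Followed as written, the plan would adjust one of the three primary-endpoint estimates towards a different population and attach an interval with no probability basis under Section 3.3.3. Section 1.1 goes further and says that every prevalence estimate will be weighted to represent the site communities.

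**Working it through.** **1. The selection descriptions side by side**

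| Section | Sample | First stage | Second stage |
|---|---|---|---|
| 1.2 | Senior living | Facilities that express interest | Census, up to 500 |
| 3.3.3 | Senior living | Interested, consenting facilities | Convenience sample, 500 |
| 3.3.1 | Community venues | Stratified random draw of venue time blocks | Individuals sampled within blocks |
| 3.3.2 | Outpatient clinics | Random draw of clinic time blocks | Individuals sampled within blocks |

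Only the senior-living sample lacks a random stage.

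**2. When a base weight exists.** Under 3.3.3 the inclusion probability is unknown, so the weight is undefined. Under 1.2 it is 1 for residents of participating facilities if those facilities house N ≤ 500 people. Otherwise 500 places cover 500/N of them. For assumed N of 500, 600, 1,000 and 2,000 the coverage is 100%, 83%, 50% and 25%, and the text does not say how the 500 are then chosen.

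**3. The protocol's own sample-size figure.** Section 6.2, Table 2, at prevalence 0.05, margin 0.025 and design effect 2.5: 2.5 × 1.96² × 0.05 × 0.95 / 0.025² = 729.9, which matches the stated 730. The total also reproduces: 4 × 730 + 500 + 500 = 3,920. The protocol derives no figure for the senior-living 500, so there is none to reproduce.

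**4. Nominal precision at n = 500.** Half-width = 1.96 × √(p(1−p)/500): 2.63 points at p = 0.10 and 3.80 points at p = 0.25. This is simple-random-sample error only.

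**5. Effect of county calibration (all inputs assumed).** Restrict the county margin to residents aged 60+. Let s be the share of the sample aged 80+, and P the share of county residents 60+ who are aged 80+. Then:

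- shift = |s − P| × the prevalence gap between the two age groups
- Kish weighting loss = P²/s + (1−P)²/(1−s)

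| s | P | Shift, 10-point gap | Shift, 5-point gap | Kish loss | Effective n |
|---|---|---|---|---|---|
| 0.50 | 0.25 | 2.5 | 1.25 | 1.25 | 400 |
| 0.60 | 0.20 | 4.0 | 2.0 | 1.67 | 300 |
| 0.70 | 0.15 | 5.5 | 2.75 | 2.44 | 205 |

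With no gap the shift is 0. It is also 0 from age adjustment if the margin stops at the protocol's own 60+ category. The weighting loss widens the 3.80-point half-width to 3.80 × √1.25 = 4.2 and 3.80 × √2.44 = 5.9 points at the two ends.

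**6. Effect of non-random selection on the interval (bias assumed).** At p = 0.10 and n = 500, SE = √(0.10 × 0.90/500) = 1.34 points. Coverage of the nominal 95% interval under bias b is Φ(1.96 − b/SE) − Φ(−1.96 − b/SE). It is 68% for a 2-point bias and 4% for a 5-point bias. With a design effect of 2.5, which the protocol assumes only for the community strata, it is 84% and 35%. The actual bias cannot be computed from the protocol.

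**The case against.** The two descriptions share the same frame of willing facilities and differ only on whether everyone in it is approached. Section 3.3.3 leaves that detail to the SSP Manual. A site could complete facilities one at a time and stop near 500, which keeps inclusion close to 1 within each surveyed facility. Section 6.3 introduces its adjustment variables only as examples and sends technical detail to a SAP, which could choose suitable control totals for each population. Inclusion criterion 3.1.1.3 already requires recruitment from a selected facility. Venues and clinics can also refuse access. Section 1.1 ties its claim of representative cohorts to time-location sampling, which is not used here. Finally, every size calculation rests on assumed inputs.

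Some of this stands. The magnitudes are illustrations, the sequential-census reading is possible, and Section 6.2 is not a third design. The rest does not remove the problem. A manual or a SAP can add detail, but one that exempted this sample would contradict Sections 6.3 and 6.3.1, which name the county-level source and include this population without qualification. An eligibility criterion does not restate the target population. Refusals limit the venue and clinic frames too, but those samples still have a random first stage. The Section 1.1 sentence on weighting covers all prevalence estimates, whatever the surrounding text implies.

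**Conclusion.** The concern holds and should be fixed. The census and convenience descriptions conflict, and neither supports the stated analysis for the target as defined. That conclusion follows from the text and needs no assumption.

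The numerical consequence is conditional. It could be nil, or it could match or exceed the nominal half-width, depending on the margins used, the age mix of the sample and how far prevalence varies with age. The scope is limited: senior living is optional by site, makes up at most 500 of 3,920 participants per site (12.8%), and is analysed separately.

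**What to change.** - **Sections 1.2, 3.3.3 and 6.2:** give one description of how residents are selected, including what happens when participating facilities house more than 500 people.
- **Sections 6.3 and 6.3.1:** exempt the senior-living sample from county census raking and post-stratification. Exempt it from base weights too, unless a census with known inclusion is actually done.
- **Reporting:** present the estimate as prevalence among residents of the participating facilities, optionally calibrated to facility rosters where counts exist. State that any 95% interval assumes ignorable participation and does not extend to other facilities.
- **Section 1.1:** qualify the sentence on weighted, representative estimates so that it does not cover this sample.

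The cost is revised wording, handled as a protocol amendment under Section 9.5, and a narrower claim for this one population. No extra participants, specimens or required data are needed.
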